3.4.2 Secondary Efficacy Variables

Secondary efficacy variables in this study are as following:

- Transplantation-free survival from fetal diagnosis to 2 years of age (analysed as time to event on FAS_{ENR} (main analysis), FAS_{BIRTH} (followed from birth), PP_{ENR} and PP_{BIRTH} (followed from birth), overall for FAV 1+2 vs no-FAV 1+2 (main analysis), and descriptively FAV 1 vs no-FAV 1 and FAV 1 vs no-FAV 1+2).
- Survival from fetal diagnosis to live birth (analysed as time to event on FAS_{ENR} (main analysis) and PP_{ENR}, overall for FAV 1+2 vs no-FAV 1+2 (main analysis), and descriptively FAV 1 vs no-FAV 1 and FAV 1 vs no-FAV 1+2).

Protocol

Statistical Analysis Plan

Effect of fetal aortic valvuloplasty on outcomes

- Proportion of included patients who have a biventricular circulation at neonatal hospital discharge (analysed on FAS_{ENR} (main analysis), FAS_{BIRTH}, PP_{ENR} and PP_{BIRTH}, overall for FAV 1+2 vs no-FAV 1+2 (main analysis), and descriptively FAV 1 vs no-FAV 1 and FAV 1 vs no-FAV 1+2).
- Proportion of included patients who have a biventricular circulation at 2 years of age (analysed on FAS_{ENR} (main analysis), FAS_{BIRTH}, PP_{ENR} and PP_{BIRTH}, overall for FAV 1+2 vs no-FAV 1+2 (main analysis), and descriptively FAV 1 vs no-FAV 1 and FAV 1 vs no-FAV 1+2).
- Number of postnatal catheter and/or surgical procedures before 2 years of age (analysed on FAS_{BIRTH} (main analysis) and PP_{BIRTH}, overall for FAV 1+2 vs no-FAV 1+2 (main analysis), and descriptively FAV 1 vs no-FAV 1 and FAV 1 vs no-FAV 1+2).

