Effect of fetal aortic valvuloplasty on outcomes

Protocol No:

screening policies) and gestational age at inclusion. Most probably they are highly correlated and in that case the more influential of the two will be used.

Variables listed under 3.1 as potential confounders will be investigated whether they are important for discriminating FAV vs no-FAV and whether they are confounders (associated p<0.10 both to the group and the outcome).

Dichotomous outcome variables will be analysed using logistic regression, adjusted for identified confounders available at the time of study inclusion. Odds-ratios (OR) with 95% confidence intervals (CI) will be presented.

Time-to-event analyses will be performed using Cox proportional hazards models adjusting for identified confounders. Proportional hazards assumption will be checked by visually reviewing log(-log(survival)) vs log(time) graphs, and by adding interaction between treatment group and log(time) in the model, where significant interaction indicates non-proportionality. Other methods will be applied, e.g. Poisson regression for time varying data, allowing study of changes in treatment effects over follow-up time, in case non-proportionality of hazards occurs.

Time-to-event data will be described by using Kaplan-Meier technique.

The primary analyses for the FAV vs no-FAV group conducted on FAS_{ENR} population will be considered as confirmatory analyses and a total significance mass of 0.05 will be applied. The tests will be performed on the primary variable and the most important secondary variables using fix sequential testing procedure according to the following order:

1. Primary variable: Transplantation-free survival from fetal diagnosis to 2 years postnatal age, having a biventricular circulation without pulmonary hypertension at that time

2. Secondary variable: Transplantation-free survival from fetal diagnosis to 2 years of age

3. Secondary variable: Survival from fetal diagnosis to live birth at term (≥37 weeks)

4. Secondary variable: Proportion of included fetuses who have a biventricular circulation at neonatal hospital discharge

5. Secondary variable: Proportion of included fetuses who have a biventricular circulation at 2 years of postnatal age

This means that first test must be significant on 0.05 significance level in order to be able to further confirm the tests 2 to 5, and the second test must be significant on 0.05 level in order to be able to confirm tests number 3 to 5, etc.

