Protocol

Statistical Analysis Plan

Effect of fetal aortic valvuloplasty on outcomes

Analysis of longitudinal change of left heart size and function, will be conducted in an exploratory manner. This will be investigated using mixed models for repeated data, with normal distribution for z-scores and binomial distribution for binary variables, handling time in study both as distinct visits and continuous (gestational age) as found most appropriate. Linear and non-linear models will be investigated. Model selection will be based on lowest goodness of fit statistics, e.g. Akaike's Information Criterion. Even though a p<0.05 the tests will not be considered confirmed, since not included in the multiplicity corrections above. Estimates, 95% CI, and p-values will be evaluated for descriptive purpose.

All tests will be two-tailed. All analyses will be performed by using SAS software version 9.4 or later (SAS Institute Inc., Cary, NC, USA).

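### Survival to live birth is planned as a time-to-event variable with no stated event and no rule for live births; neither the curve nor the hazard ratio would estimate the proportion born alive, and confirmatory test 3 names a different variable

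*SAP*

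**What the plan says.** SAP 3.4.2 lists among the secondary efficacy variables "Survival from fetal diagnosis to live birth (analysed as time to event on" the enrolled full analysis set and the enrolled per-protocol set).

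SAP 4.1 gives the methods for that type of variable: "Time-to-event analyses will be performed using Cox proportional hazards models adjusting for identified confounders", and "Time-to-event data will be described by using Kaplan-Meier technique". It adds a proportional-hazards check and names Poisson regression as one fallback.

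The third test in the fixed sequence of SAP 4.1 is worded differently: "Survival from fetal diagnosis to live birth at term (≥37 weeks"). The sequence runs under a family level where "a total significance mass of 0.05 will be applied", and "the second test must be significant on 0.05 level in order to be able to confirm tests number 3 to 5".

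Neither document states what the event is, whether a live birth is censored, an event or a competing event, how a preterm live birth counts in test 3, or which model test 3 uses. SAP 3.4.1 does explain why the primary variable cannot be time to event (two of its components are assessed at age 2 years). No comparable reasoning is given for this variable.

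**The concern.** Every fetus that does not die in utero leaves the risk set by being born, and that is the success the variable names. A standard survival analysis has no place for such an exit. Censoring it treats born infants as if they could still die in utero later. Because time runs from diagnosis and birth comes at a different time for each fetus, no single point on the curve equals the proportion born alive. A Cox model on the same data compares death rates per week of remaining pregnancy.

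The two groups may well differ in length of gestation and in the timing of deaths. The plan itself lists preterm delivery, and fetal death within 24 hours of the procedure, as safety variables. At stake are a secondary efficacy result that readers will take as the share of fetuses reaching live birth and, if tests 1 and 2 succeed, a confirmatory test whose outcome and model are not settled.

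**Working it through.** **Inputs.** From the documents: the variable and its type (SAP 3.4.2), the methods and test order (SAP 4.1), and the planned 100 FAV and 50 no-FAV cases (SAP 1.5). The documents give no fetal loss rate, delivery timing or age at diagnosis for this variable, so every rate below is an assumption.

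**The plan's own figures.** There is none for this variable. The stated powers of 91.8% and 98.7% concern the primary variable. An arcsine approximation to Fisher's test gives 91.84% and 98.69%, and exact enumeration gives 92.7% and 98.9%. There is no error there, and these figures do not bear on this point.

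**1. Curve, with fetal death as the event and births censored.** For a constant weekly hazard h and w weeks from diagnosis to birth, actual loss is about 1 − exp(−h·w). One minus Kaplan-Meier at week t estimates 1 − exp(−h·t), and late in the curve t exceeds the average w. Take h = 0.05/13.5 = 0.0037, diagnosis at 25 weeks and mean birth at 39 weeks (SD 1.5).

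- Actual loss (w = 14): 1 − exp(−0.0519) = 5.1%. Curve at 41 weeks (t = 16): 1 − exp(−0.0593) = 5.8%. Excess 0.7 points; simulation gives the same two figures.
- With 10% early procedural deaths: 1 − 0.9·exp(−0.0519) = 14.5% actual, and 1 − 0.9·exp(−0.0593) = 15.2% on the curve.
- With the hazard rising fourfold after 37 weeks (simulated): 10.3–10.6% on the curve at 41.5 weeks against 7.1–7.2% actual.
- With diagnosis spread evenly over 19–30 weeks, birth at about 38.5 weeks and a constant hazard (simulated): mean 9.0% at the end of the curve against 6.2% actual, an excess of 2.8 points. In a similar run with cohorts of 50, the mean was 8.7% against 5.9%, but the median excess was 0.7 points and the curve at week 16 read 6.8%. The excess sits in the tail, where few remain at risk.

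**2. Hazard ratio, equal weekly death hazards.** Constant h as above, no-FAV births at 39 weeks, FAV births moved earlier (simulated; standard error of the log hazard ratio about 0.017). The last column uses a different event: fetal death or birth before 37 weeks.

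| FAV mean birth (weeks) | HR, fetal death | Actual loss FAV / no-FAV | Risk ratio | HR, death or birth <37 weeks |
|---|---|---|---|---|
| 39 | 1.00 | 5.1% / 5.1% | 1.00 | 1.00 |
| 38 | 0.99 | 4.7% / 5.1% | 0.92 | 2.38 |
| 37 | 0.98 | 4.3% / 5.1% | 0.84 | 5.24 |
| 36 | 0.98 | 4.0% / 5.1% | 0.78 | 10.1 |

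The fetal-death hazard ratio stays near 1 while the actual proportions separate.

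Hand check of the last column at 37 weeks: term success is P(birth ≥37 weeks) × exp(−12h), that is 0.909 × 0.957 = 0.869 for no-FAV and 0.500 × 0.957 = 0.478 for FAV. Then ln(0.478)/ln(0.869) = 0.738/0.140 ≈ 5.3.

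**3. Hazard ratio, equal proportions lost.** With constant hazards and equal loss, the hazard ratio is close to the inverse ratio of mean weeks at risk. Diagnosis averaging 24.5 weeks and birth at 38.5 weeks give 14 weeks. Delivery 1, 2 or 2.5 weeks earlier in FAV gives 14/13 = 1.08, 14/12 = 1.17 and 14/11.5 = 1.22. Fitted Cox models gave about 1.06 to 1.21 over this range.

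**4. Live birth as the event.** With equal death hazards and FAV births two weeks earlier, the hazard ratio is about 3.5. It measures delivery timing.

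**5. The two definitions side by side.** SAP 3.4.2 counts any live birth. Test 3 in SAP 4.1 requires birth at 37 weeks or later. A preterm live birth is a success under the first and, on the face of the wording, not under the second. In step 2 the first makes earlier delivery look neutral or favourable, and the second makes it dominate the comparison against FAV.

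**The case against.** The strongest reply is that a Cox model with births censored gives a legitimate cause-specific hazard ratio, so that preferring the proportion born alive is a choice between estimands. That stands as far as it goes. But the variable is named as survival to live birth and the SAP does not say that a weekly death rate is intended.

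A reader might infer that earlier delivery by itself shifts the hazard ratio against FAV. The working does not support this: with equal, constant weekly hazards the ratio stays near 1. The ratios above 1 in step 3 reflect a higher weekly death rate, which equal loss over a shorter time implies, so they are not a bias of the model. When hazards are not constant the ratio can move either way. With 10% early procedural deaths it went from 3.07 to 3.38 as FAV delivery moved from 39 to 36 weeks, while the risk ratio fell from 2.86 to 2.68. With the hazard rising fourfold after 37 weeks and diagnosis ages spread, FAV delivery 1 or 2 weeks earlier gave 0.94 and 0.88. The planned proportional-hazards check partly covers such cases, but the named Poisson fallback still models a rate.

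It is also fair that censoring of births is inferred, because the SAP is silent. Each alternative coding (steps 2 and 4) moves further from the proportion born alive, so the silence does not rescue the analysis.

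Finally, reach is limited. Kaplan-Meier is descriptive here. Fetal deaths are described by group (SAP 4.7.3), and the counts in the two full analysis sets (SAP 4.2) give the crude live-birth proportion. Those figures are unadjusted, however, and SAP 4.1 calls for adjustment because the groups are not randomised.

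**Conclusion.** The point holds as a defect of definition and method in a secondary variable; it should be corrected before analysis.

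- **Curve.** If births are censored, one minus Kaplan-Meier overstates fetal loss by a mean of about 1 to 3 points under a constant hazard, and by more if the hazard rises near term. The excess is concentrated at the end of the curve. The median excess under a constant hazard was below 1 point in cohorts of 50.
- **Hazard ratio.** It does not track the proportion born alive when delivery timing differs. If live birth or preterm birth is the event, it mainly reflects delivery timing.
- **Test 3.** A reader might take the variable in SAP 3.4.2 to be confirmatory test 3. It is not, as worded: test 3 adds the term condition. Test 3 is confirmatory only if tests 1 and 2 are both significant; it would then gate tests 4 and 5.

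All sizes rest on assumed loss rates, diagnosis ages and delivery times. The direction of the curve's error needs only that births are censored and that some fetal deaths occur after births have begun.

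**What to change.** 1. Use one definition in SAP 3.4.2 and in test 3 of SAP 4.1, and state whether a preterm live birth counts as success. If both versions are wanted, list them as two variables and say which is test 3.
2. Analyse the chosen variable as yes/no with the adjusted logistic regression that SAP 4.1 already specifies for dichotomous outcomes, using the same confounders.
3. If a time course is wanted, show the cumulative incidence of fetal death with live birth as a competing event in place of one minus Kaplan-Meier.
4. If a hazard ratio is kept as a supplement, state its event and how births are handled, and describe it as a comparison of weekly death rates.

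The cost is wording in two SAP sections; no new data are needed. There are two downsides: the timing of fetal death is then only described, and pregnancies lost to follow-up need a stated handling.

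The change does not add information where deaths are few. At an assumed 5% loss, 150 cases give 150 × 0.05 = 7.5 deaths, so either model can carry few confounders if failure means fetal death.

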2.1.2 Full Analysis Set for Live Births Intended for Postnatal Treatment

All enrolled fetuses that have satisfied inclusion/exclusion criteria and belong to FAV 1+2 and no-FAV 1+2 groups and not listed as the high-risk population above that also are live at birth will be included in the Full Analysis Set at birth (FAS_{BIRTH}) population. Infants wrongly included in the study will not be part of the FAS_{BIRTH} population, but will be described in the safety analyses.

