4 STATISTICAL METHODOLOGY

4.1 General Methodology

Continuous variables will be described by means, standard deviation (SD), median and range, and categorical by number and percentages.

Main analyses will be performed comparing FAV 1+2 versus no-FAV 1+2 groups on FAS_{ENR} population. Complementary analyses will be performed on FAS_{BIRTH}, PP_{ENR} and PP_{BIRTH}. Separate descriptive comparisons between FAV 1 vs no-FAV 1 and FAV 1 vs no-FAV 1+2 groups will also be performed.

Comparisons between the two groups with respect to demographics and baseline characteristics and safety data will be performed using Fisher's exact test for dichotomous variables, Mantel-Haenszel Chi-square test for ordered categorical variables, Chi-square test for non-ordered categorical variables, and Fisher's non-parametric permutation test for continuous variables.

Due to the non-randomised design, all analyses will be adjusted for confounders. It is important that all known confounders at the time of inclusion are defined. The main confounders will be gestational age at first diagnosis and at inclusion, morphology and hemodynamics of the fetal heart at the time of study inclusion and possibly some data about the mother's health which could have an impact on the chance of success with fetal intervention, such as BMI. Although the study is designed to minimize bias by using strict echocardiographic inclusion criteria, it will be necessary to analyse the groups at baseline carefully with respect to a number of selected echocardiographic variables describing the size and function of the left heart. If this analysis shows that, in spite of the strict inclusion criteria, there are significant differences between the groups regarding data that are at the same time risk factors for the studied outcomes the analyses will be adjusted for those additionally defined confounders besides the known ones. A sensitivity analysis will also be performed for the primary variable applying propensity score matching procedure (1:1 or 2:1 if possible) including all variables that are of importance (p<0.10 using logistic regression) for discrimination of FAV vs no-FAV group and those identified/known confounders in the adjusted analyses.

Known confounders are:

• Gestational age at primary diagnosis (earlier gestational age could indicate more severe disease, and might differ between countries and centres due to different

Protocol

Statistical Analysis Plan

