4.6.2 Secondary Efficacy Analyses

Secondary variables will be analysed according to described methods in General Methodology above.

STATISTISKA KONSULTGRUPPEN	Statisti	cal Analysis Plan
Effect of fetal aortic valvuloplasty on outcomes	Protocol No):
	Version:	

1.0 Page 24 of 26

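### The postnatal procedure count to age 2 has no stated analysis and no rule for death, so the group with more infant deaths can appear less burdened

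*SAP*

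**What the plan says.** SAP 3.4.2 lists five secondary efficacy variables. The last is "Number of postnatal catheter and/or surgical procedures before 2 years of age". Its main analysis compares FAV 1+2 with no-FAV 1+2 on FAS_BIRTH, and PP_BIRTH is the other set.

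SAP 2.1.2 defines FAS_BIRTH as eligible fetuses in the FAV and no-FAV groups, outside the high-risk population, "that also are live at birth will be included in the Full Analysis Set at birth". Survival to age 2 is not required, so an infant who dies stays in the set with whatever count had accrued.

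On method, SAP 4.6.2 says only: "Secondary variables will be analysed according to described methods in General Methodology above". SAP 4.1 then offers:

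- a general rule: "Due to the non-randomised design, all analyses will be adjusted for confounders";
- for binary outcomes: "Dichotomous outcome variables will be analysed using logistic regression, adjusted for identified confounders available at the time of study inclusion";
- for survival outcomes: "Time-to-event analyses will be performed using Cox proportional hazards models adjusting for identified confounders";
- a fallback if hazards are not proportional: "Other methods will be applied, e.g. Poisson regression for time varying data";
- for demographic, baseline and safety comparisons of numeric data, a "non-parametric permutation test for continuous variables";
- exploratory mixed models for the longitudinal echo measurements.

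None of these is assigned to a count used as an efficacy outcome. SAP 3.4.1 makes death part of the primary composite, and 3.4.2 analyses transplantation-free survival as time to event. The count has no corresponding rule.

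**The concern.** A count of procedures to a fixed age can only grow while the child is alive. A child who dies in the first weeks after one procedure contributes 1, and a child who survives a staged surgical course contributes several. Because the variable is classed as efficacy, a lower count will naturally be read as benefit. On that scale an early death is a good result.

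Adjustment under 4.1 does not help. It uses confounders present at inclusion, whereas death here comes after birth and may itself be affected by the fetal procedure. An effect on survival is one of the plan's own hypotheses (second in the 4.1 testing order), so a difference in mortality between groups is a realistic case. If FAV improves infant survival, its group could show the higher burden. If FAV worsens survival, its group could show a saving.

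**Working it through.** The plan states no figure for this variable. Its power statement in SAP 1.5 concerns the primary endpoint only, so there is nothing to reproduce. The documents also give no postnatal mortality and no procedures per child. All inputs below are therefore assumptions, with care identical in the two groups.

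**1. Early deaths.** Survivors have 3 procedures. Early deaths have 1 (or 0). With proportion *d* dying, the mean count is 3(1−d) + 1·d, or 3(1−d) if deaths have none.

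| d | Deaths have 1 | Change from d = 10% | Deaths have 0 | Change from d = 10% |
|---|---|---|---|---|
| 10% | 2.8 | – | 2.7 | – |
| 20% | 2.6 | 7% lower | 2.4 | 11% lower |
| 30% | 2.4 | 14% lower | 2.1 | 22% lower |
| 40% | 2.2 | 21% lower | 1.8 | 33% lower |

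For example, 2.4/2.8 = 0.857.

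**2. Deaths spread over two years.** With a constant death hazard, mean time alive is 2d/(−ln(1−d)): 1.898, 1.793, 1.682 and 1.566 years for d = 10%, 20%, 30% and 40%. At 1.5 procedures per year alive, the mean counts are 2.85, 2.69, 2.52 and 2.35. Relative to 10% deaths the ratios are 0.944, 0.886 and 0.825.

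In 2,000 simulated trials of 100 versus 50 under this setting, a t-test on the count rejected at nominal 5% in:

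- 4.9% of trials with 10% deaths in both groups;
- 8% with 10% versus 20%;
- 18% with 10% versus 30%;
- 38% with 10% versus 40%.

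A comparison per unit of time alive rejected in about 5% throughout.

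**3. Is a rate per time alive sufficient?** Step 2 favours it because the procedure rate was simulated as constant. In the step 1 setting, with 1 procedure in early deaths and those deaths at 1 month:

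- 10% deaths: mean time alive = 0.9×2 + 0.1/12 = 1.808 years, rate 2.8/1.808 = 1.55 per year.
- 30% deaths: mean time alive = 0.7×2 + 0.3/12 = 1.425 years, rate 2.4/1.425 = 1.68 per year.

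The ratio is 1.09 (1.10 with deaths at 2 weeks, 1.07 at 2 months). The spurious saving becomes a spurious excess, so a rate cannot be the main analysis.

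**4. Ranking death as worst.** Use the same example (1 procedure in deaths), with group A at 10% deaths and group B at 30%, and take one child at random from each.

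- By count alone, B looks better with probability 0.9×0.3 = 0.27 and A with 0.1×0.7 = 0.07.
- With death ranked worst, these reverse: A is better with probability 0.27 and B with 0.07. The rest are ties.

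The ordering no longer rewards death. In this example the difference is due wholly to mortality, which is why the components must be shown too.

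**The case against.** The best defence is that the consequence is small and visible. The count is not among the five confirmatory tests in SAP 4.1. Transplantation-free survival is analysed from birth on the same FAS_BIRTH set (3.4.2), reasons for death are described by group (4.7.3), and death is a failure in the primary composite (3.4.1). A careful reader would see excess deaths next to a lower count. The bias also needs a mortality difference: with 10% deaths in both groups the simulated rejection rate is 4.9%. All of this stands and limits the weight of the point.

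Three stronger readings are tempting, and the documents do not support them.

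- A reader might infer that the SAP plans an unadjusted comparison of raw counts by permutation test, in breach of its own adjustment rule. It does not say so. That test is assigned to demographic, baseline and safety data. The fair reading of 4.1 is an adjusted analysis whose model is not named.
- A reader might infer that this is the trial's only measure of postnatal burden. SAP 3.5.4, 4.5 and 4.7.4 also list or describe postnatal interventions by group. These outputs are descriptive and have no death rule either, but they exist.
- A reader might infer that the plan would conceal excess mortality behind an apparent saving. The survival outputs above make that unlikely.

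A mean cumulative count with death as a terminal event might be offered as a remedy. With complete follow-up to age 2 it equals the raw mean count, so it does not remove the problem.

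**Conclusion.** The point holds as a gap with a known direction. The chosen variable and analysis set let death truncate the outcome in the direction that looks favourable, and the SAP supplies neither a count model nor a death rule to deal with it. Baseline adjustment cannot repair this, so it is more than missing detail.

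On the assumed inputs, a mortality contrast of 10% versus 20–40% produces an apparent reduction of about 6% to 33% under identical care. The reference case, 10% versus 30% with 1 procedure in early deaths, gives 14%. The size depends entirely on assumed mortality and procedure numbers. The direction assumes that fewer procedures is read as better and that children who die have had fewer procedures than survivors. It would not hold if they had as many or more. With equal mortality the bias is zero. Because no confirmatory claim depends on the variable, the change should be made but is not critical.

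**What to change.** Amend SAP 3.4.2 and 4.6.2 as follows.

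1. Analyse the outcome with a confounder-adjusted ordinal (proportional odds) model. Death or transplantation before age 2 is the worst rank, and all other children are ranked by number of procedures.
2. Beside it, show by group the deaths and transplantations before age 2, the count in all live births, and the count in children alive and untransplanted at age 2. Label the last as descriptive, because it conditions on survival.
3. State that no conclusion of lower burden will be drawn from the all-live-births count alone.
4. Allow a rate per time alive only as a supplementary analysis, noting that it overstates burden in early deaths when procedures cluster after birth.

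The cost is SAP wording and one model. The eCRFs for postnatal procedures and subject termination already exist, and the planned transplantation-free survival analysis already needs death and transplantation times. The drawback is that the ranked outcome is partly driven by mortality and is harder to explain than a mean count. Showing the components in item 2 addresses this.
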